6. EXPECTED RESULTS

After this study, we hope to understand the efficacy and safety of ivermectin for the treatment of adult patients with mild SARS CoV 2 disease.

| Amendment 2 to the Study Protocol_August 04, 2020. | 
a. The title was changed: The study was extended to other municipalities in Valle del Cauca near the capital.
 
B. Included: the use of SARS-CoV-2 antigen detection in nasopharyngeal sample.
 
C. A secondary objective was added: the duration of fever as an indirect marker of the antiviral capacity of the drug.
 
d. Placebo produced by Tecnoquimicas laboratory was included.
 
e. Changed: Onset of SARS CoV2 / COVID 19 illness 7 days ago or less.
 
f. Liver tests taken within 3 days were included.
 
g. The range of liver enzymes was increased ≥ 1.5
 
h. Order of procedures was corrected
 | 
1. Due to the difficulty in identifying subjects in the city of Cali, we will extend the study to other municipalities in Valle del Cauca near the capital.
 
2. Due to the congestion of health services due to COVID-19 and the high demand for testing, the opportunity for RT-PCR reporting is scarce and the results of a patient are usually available after 5 days of taking it. In May 2020 and August 2020, the FDA (United States) and the Ministry of Health of Colombia, respectively, have approved the use of antigen detection as valid diagnostic tests for the diagnosis of COVID-19. Through this amendment we intend to identify subjects in the initial stages of the disease and improve the recruitment of subjects, this is included in the inclusion criteria.
 
3. Duration of fever: This secondary objective is added as an indirect marker of the antiviral capacity of the drug.
 
4. The placebo was changed from 5% dextrose to placebo: in the process of elaboration of the protocol, the pharmaceutical laboratory that produces the investigation product did not confirm that it could produce the placebo with the same characteristics but without active ingredient. Only until now we have been informed that they can produce it, for this reason this final amendment 2 from July 17, 2020 is included and the Investigator's manual is updated.
 
5. Inclusion criteria: it is increased to 7 days, taking into account that during the elaboration of the protocol until now, it is very difficult to obtain the tests results within 5 days due to high demand in the laboratories that process the samples. By broadening this selection criterion, the objective of making an intervention in the earliest stage of the disease is maintained, allowing us to reach the proposed sample size.
 
6. Exclusion criterion: The increase in the elevation range from 1.25 to 1.5 times is generated because we are having a large number of subjects with screening failures due to minimal elevations in liver enzymes. These elevations are usually transitory and produced by conditions other than liver pathologies (produced by puncture, injections, mild trauma, stress from acute infection, use of other medications, fatty foods, laboratory errors, etc.). For this reason, increasing the elevation range from 1.25 to 1.5 times does not increase risks for the subject when entering the study.
 
7. Selection criterion: The range of liver enzymes was increased > 1.5: We found that some subjects may have recent reliable liver enzyme test results within the established time frame (days prior to screening). We can decrease the risk involved in a puncture (bruising, infection, etc.) and yet we can verify the exclusion criteria indicated in the protocol with these recent tests.
 
8. Exclusion criterion: Patients with progressive improvement of symptoms: This criterion is added taking into account that we extended the inclusion criterion to 7 days. However, subjects who present progressive improvement between days 5-7 are at low risk of clinical deterioration. Thus their inclusion would reduce the power of the study.
 
9. Table of visits and procedures: the name of visits is changed. This change is justified in that they can be carried out on the same day.
 | New ICF issued Informed Consent Format and General Informed Consent of the study, Version 5.0 of August 04, 2020. | Approved by INVIMA on August 27, 2020: |
| Final Amendment 3 to the Study Protocol_September 16, 2020 | 
a. This specific objective was included: "To compare the time between randomization and disappearance of symptoms in subjects receiving the D11AX22 molecule (ivermectin) vs. Placebo"
 
b. The original primary outcome was changed to: "To determine the time until the resolution of the symptoms in the two study groups."
 
c. The original primary outcome becomes a secondary outcome
 | 
Less than 3% of the subjects included to date have had the primary outcome described in Amendment 2 ("To determine the time to deterioration in two or more points of the 7-point ordinal scale in the two study groups."). If this primary outcome were retained, the sample size to obtain adequate statistical power would be unattainable (more than 2000 subjects).
 
With this amendment we intend to meet the general and specific objectives with the initially proposed sample size.
 | No new ICF issued | Approved by INVIMA on November 06, 2020 |
| Final Amendment 4 to the Study Protocol_October 27, 2020 | 
a. Sample size increased to 476
 | 
After the start of the study, 38 subjects who were randomized to receive placebo were given ivermectin by mistake in the enrollment of the investigation product. This occurred consecutively over a period of three weeks, so during this period a total of 76 subjects received ivermectin and none received a placebo.
 
This situation was discussed with the independent data monitoring board. Taking into account that this is a systematic error, in which none of these participants received the randomly assigned investigation product, the exclusion of these 76 subjects from the primary analysis was decided. To preserve the planned sample of 400 subjects and thus preserve the statistical power of the study, an additional 76 participants will be included for a total of 476 participants. The 76 participants excluded from the primary analysis will complete the follow-up established by the protocol.
 | INFORMED CONSENT FORM AND GENERAL INFORMED CONSENT OF THE STUDY_Version 6.0_476 October 27, 2020 | Approved by INVIMA on November 9, 2020: |

Statistical Analysis Plan

(SAP)

| | |
|------------------------|---|
| Protocol Title | Double blind, randomized, controlled clinical trial to investigate the effectiveness of the d11ax22 molecule in adult subjects from Valle del Cauca with initial stages of infection by SARS-CoV-2/ Covid-19. |
| Acronym | EPIC |
| Protocol version | Final Version 2.0: May 12, 2020 |
| ClinicalTrials.gov | NCT04405843 |
| Principal Investigator | [name] [name], MD, MSc Centro de Estudios en Infectología Pediátrica Universidad del Valle Clinica Imbanaco |
| Author | [name], BSc, MSc |
| Version | Jun 7, 2020 |

Abbreviations

| | |
|-----|---------------------------|
| ECC | Controlled Clinical Trial |
| ICU | Intensive Care Unit |
| ITT | Intension to treat |
| PP | Per protocol |

Table of contents

| | |
|---|----------|
| 1. Introduction | 4 |
| 2. Study Design | 4 |
| 2.1. Interventions..... | 4 |
| 2.2. Sample size calculation | 5 |
| 3. Study Aim | 5 |
| To describe the efficacy of the D11AX22 (ivermectin) molecule in adults with mild COVID-19 disease..... | 5 |
| 4. Outcomes | 5 |
| 4.1. Primary outcome..... | 5 |
| 4.2. Secondary outcomes | 6 |
| 4.3. Safety outcomes..... | 6 |
| 5. Study population and subgroup analysis | 6 |
| 5.1. Populations | 6 |
| 5.2. Subgroups | 7 |
| 6. Analysis plan | 7 |
| 6.1. Primary outcome..... | 7 |
| 6.2. Secondary outcomes | 8 |
| 6.3. Sensitivity Analysis and Modification of the Effect for the Primary outcome. | 9 |
| 6.4. Safety analysis..... | 9 |
| 6.5. Handling missing data..... | 9 |

1. Introduction

The purpose of this study is to assess whether D11AX22 molecule (ivermectin) reduces the time until worsening in 2 or more points in the 7-point ordinal scale (primary outcome variable), as well as the proportion of patients who require hospitalization, use of supplementary oxygen and intensive care (secondary outcome variables), compared to placebo in subjects with mild COVID-19 disease. This document describes definitions and statistical methods to be used in order to fulfill EPIC trial aim and objectives.

2. Study Design

Double-blind, randomized, placebo-controlled clinical trial to evaluate the efficacy of the D11AX22 (ivermectin) molecule in adult subjects with mild SARS CoV2/COVID-19 disease at participating institutions in Valle del Cauca.

This study is a controlled clinical trial with two parallel group with an allocation ratio of 1:1. Ten clinical visits will be made at the following times: day 0 (visit 1), day 1 (visit 2) day 2, day 3, day 4, day 5, day 8, day 11, day 15 and day 21.

2.1. Interventions

Intervention group or treatment: Participants assigned to **ivermectin**, once a day for 5 days.

Treatment name: Molecule D11AX22 (ivermectin)

Drug name: ivermectin

Drug presentation: oral drops in suspension 6 mg / ml.

Route of administration: oral

Primary container: 5mL bottle

Volume to be administered: depends on the patient's weight

Dose: 300 mcg/kg/day

Storage conditions on the label: room temperature

Indications for administration: preferably a single dose on an empty stomach, with water.

Serious interactions: Warfarin, erdafitinib, quinidine

Control Group: Participants assigned to **placebo**, once a day for five days.

Treatment name: placebo

Drug Name: 5% Dextrose

Drug Presentation: solution

Route of administration: oral

Primary container: 5mL bottle

Volume to be administered: depends on the patient's weight

Dose: same volume that would be administered of ivermectin to maintain the blind

Storage conditions on the label: room temperature

Indications for administration: same as ivermectin.

2.2. Sample size calculation

According to the literature, 20% of patients will develop the primary outcome (worsening of 2 or more points in the 7-point ordinal scale). Thus, we will need to include 400 patients (72 total events plus 10% lost events) in order to detect a Hazard ratio of 0.5 of ivermectin vs. placebo in time to deterioration, with a power of 80% and alpha of 0.05

3. Study Aim

To describe the efficacy of the D11AX22 (ivermectin) molecule in adults with mild COVID-19 disease

4. Outcomes

4.1. Primary outcome

-Time until clinical worsening in the two study groups: Number of days from randomization visit to the first day when a patient worsens 2 or more points in the 7-point ordinal scale in the two study groups. Variable measured during the 21 days of follow-up.

4.2. Secondary outcomes

-Proportion of cases that require hospitalization, use of supplemental oxygen > 24 hours, and admission to the ICU.

-Duration of hospitalization, use of supplemental oxygen and duration of stay in ICU in each arm of the study.

-Clinical state, using the 8-point ordinal scale, on days 2, 5, 8, 11, 15, and 21.

4.3. Safety outcomes

-Proportion of subjects who develop adverse events and serious adverse events associated with the study drug: patients who during follow-up report episodes of uncontrollable tremor, dizziness, loss of appetite, nausea, vomiting, stomach pain, bloating, diarrhea, constipation, weakness, drowsiness, chest discomfort, edema (face, arms, hands, feet, ankles or calves), pain and swelling in the joints, painful and swollen glands in the neck, armpit or groin, fast heartbeat, eye pain, blurred vision, redness or tearing, swelling of the eyes or the eyelids, abnormal sensation in the eyes, fever, blistering or peeling of the skin, rash, hives, and itching.

-Proportion of subjects who required discontinuation of medication due to adverse events.

5. Study population and subgroup analysis

5.1. Populations

Intention to Treat (ITT). It is the primary population of the EPIC trial and includes all patients randomized in the study. They will be analyzed according to the group assigned at the randomization visit, regardless of whether they received the medication or not.

Per protocol (PP). All patients who were adherent to the assigned intervention at the time of randomization. In addition, it includes all patients with complete data. It will be considered as a sensitivity analysis.

5.2. Subgroups

No subgroup analysis will be done.

6. Analysis plan

Initially, all the variables will be described according to the intervention groups in the ITT population. Variables with a normal distribution will be summarized with mean and standard deviation (SD), otherwise, they will be shown with median and interquartile range (IQR). Normal distribution assumption will be evaluated using the Shapiro Wilk test. All analyzes will be done in Stata 14.0® (StataCorp, College Station, Texas, USA).

6.1. Primary outcome

The main analysis will be the survival analysis for the primary outcome variable (time to deterioration in 2 or more points in the 7-point ordinal scale) using the log-rank test to compare ivermectin versus placebo as a control group. Deterioration or worsening will be assessed using the 7-point ordinal scale, which has the following categories: (1) -Non-hospitalized patient, with the ability to do daily activities, (2) -Non-hospitalized patient, unable to do daily activities, or using oxygen at home (3) -Hospitalized, without need for supplemental oxygen, (4) -Hospitalized, with need for supplemental oxygen, (5) -Hospitalized, with need for high-flow nasal oxygen or non-invasive mechanical ventilation, (6) -Hospitalized, in need of mechanical ventilation or ECMO, (7) -Death.

The outcome variable will be the time to worsening, defined as the first day, during the 21 days of follow-up, in which the patient reports an increase of 2 or more points in the ordinal scale as compared with the baseline score when randomized.

Patients who do not report deterioration in 2 or more points and those who die during study follow-up will be considered as censor data on day 21 or until death. Kaplan-Meier estimator will be used to report the recovery percentage throughout the follow-up and at

day 21. Relevant treatment efficacy parameter is the recovery hazard ratio (HR) with its respective 95% confidence interval (CI), which will be estimated by Cox proportional-hazard model. Given that the primary outcome may take two values; equal to 1 when the patient reports deterioration and 0 when not, a $HR < 1$ will indicate a favorable result for ivermectin compared to placebo.

6.2. Secondary outcomes

Secondary outcomes, hospitalization requirement, ICU or oxygen supplementation will be analyzed through a Kaplan Meier estimate. Hazard ratio will be estimated by Cox proportional-hazard model. In addition, a logistic regression model in which each secondary outcome will be considered as the dependent variable (1: Event, 0: No event) and the intervention groups as the independent variable (1: ivermectin, 0: Placebo) will be used.

For each outcome, the odds ratio (OR) and its respective 95% CI will be reported. An $OR > 1$ is indicating favorable results in favor of placebo and an $OR < 1$ in favor of ivermectin. Evaluation of the effect of the treatment in each study visit using the 7-point ordinal scale will be estimated using the proportional OR with its respective 95% CI with an ordinal logistic regression. In this step, the 7-point ordinal scale will be inverted in its score, where 1 will correspond to death and 7 to a subject without symptoms. Thus, a proportional $OR > 1$ will indicate an effect in favor of ivermectin. The 95% confidence interval of the median difference in length of hospitalization or oxygen use will be estimated by bootstrap estimators.

To further determine the efficacy of the intervention in secondary outcomes, a bivariate analysis will be performed adjusting for demographic and clinical variables. For dichotomous variables, a logistic regression will be performed and the adjusted odds ratio will be reported. For time to event variables, an adjusted cox regression model will be performed and the hazard ration will be reported. In either case, the measure of effect will be reported with its respective 95% CI.

6.3. Sensitivity Analysis and Modification of the Effect for the Primary outcome.

The analysis of the primary outcome will be repeated using the population under the per protocol approach and will be considered as sensitivity analysis. Additionally, if differences are found between the research product and the outcomes, it will be evaluated whether variables such as enrollment score on the 7-point scale, duration of symptoms before enrollment, comorbidities, age and sex, modify the effect of the intervention groups, using a multivariate Cox proportional hazards model. This will be done by including interaction terms to the model between the possible modifying variable and the intervention groups. A p value <0.10 will be considered as a possible modifying effect, and a p value <0.05 will be considered as a cut-off point to confirm a significant interaction and therefore, to estimate the effect of the treatment groups with their respective 95% CI.

6.4. Safety analysis

This analysis will be carried out on an exploratory basis and the frequency and detailed description of each adverse event will be reported.

6.5. Handling missing data

Primary outcome:

The primary outcome is expected to be available in all patients. In the event that the patient dies during follow-up, a censoring for the study will be considered until the time of last observation. If the patient is lost to follow-up, last report on the 7-point scale during follow-up will be considered as the outcome.

Covariates: If there are missing data in the variables needed to analyze for effect modification, and this may have an effect the primary outcomes of the study, then simple imputation will be performed using the median of the treatment group to which the observation belongs based on the information reported in the sample with complete data.

Secondary outcomes. Data will not be imputed. The percentage of missing data will be reported.

Statistical Analysis Plan (SAP)

| | |
|------------------------|---|
| Protocol Title | Double blind, randomized, controlled clinical trial to investigate the effectiveness of the d11ax22 molecule in adult subjects from Valle del Cauca with initial stages of infection by SARS-CoV-2/ Covid-19. |
| Acronym | EPIC |
| Protocol version | Final amendment 3, September 16, 2020 |
| ClinicalTrials.gov | NCT04405843 |
| Principal Investigator | [name] [name], MD, MSc Centro de Estudios en Infectología Pediátrica Universidad del Valle Clinica Imbanaco |
| Author | [name], BSc, MSc |
| Version | PAE 1.0, Sep 20 2020 |

Abbreviations

| | |
|-----|---------------------------|
| ECC | Controlled Clinical Trial |
| ICU | Intensive Care Unit |
| ITT | Intension to treat |
| PP | Per protocol |

Table of contents

| | |
|---|--------------------------------------|
| 1. Introduction | 4 |
| 2. Study Design | ¡Error! Marcador no definido. |
| 2.1. Interventions | 4 |
| 2.2. Sample Size Calculation..... | ¡Error! Marcador no definido. |
| 3. Study Aim | ¡Error! Marcador no definido. |
| 4. Outcomes | ¡Error! Marcador no definido. |
| 4.1. Primary Outcome..... | ¡Error! Marcador no definido. |
| 4.2. Secondary Outcomes | ¡Error! Marcador no definido. |
| 4.3. Safety Outcomes..... | ¡Error! Marcador no definido. |
| 5. Study Population and Subgroup Analysis | ¡Error! Marcador no definido. |
| 5.1. Populations | ¡Error! Marcador no definido. |
| 5.2. Subgroups | 7 |
| 6. Analysis Plan | ¡Error! Marcador no definido. |
| 6.1. Primary Outcome..... | ¡Error! Marcador no definido. |
| 6.2. Secondary Outcomes | ¡Error! Marcador no definido. |
| 6.3. Sensitivity Analysis and Modification of the Effect for the Primary Outcome | 9 |
| 6.4. Safety Analysis | ¡Error! Marcador no definido. |
| 6.5. Handling Missing Data..... | ¡Error! Marcador no definido. |

1. Introduction

The purpose of this study is to assess whether D11AX22 molecule (ivermectin) reduces the time to resolution of symptoms (primary outcome variable), as well as the proportion of hospitalization, use of supplementary oxygen and number of cases with fever or more than two points on the eight-point ordinal scale for COVID (secondary outcome variables), compared to placebo in subjects with mild COVID-19 disease. This document describes definitions and statistical methods to be used in order to fulfill EPIC trial aim and objectives.

2. Study Design

Double-blind, randomized, placebo-controlled clinical trial to evaluate the efficacy of the D11AX22 (ivermectin) molecule in adult subjects with mild SARS CoV2/COVID-19 disease at participating institutions in Valle del Cauca.

This study is a controlled clinical trial with two parallel group with an allocation ratio of 1:1. Ten clinical visits will be made at the following times: screening visit, randomization visit, day 2, day 3, day 4, day 5, day 8, day 11, day 15 and day 21.

2.1. Interventions

Intervention group or treatment: Participants assigned to **ivermectin**, once a day for 5 days.

Treatment name: Molecule D11AX22 (ivermectin)

Drug name: ivermectin

Drug presentation: oral drops in suspension 6 mg / ml.

Route of administration: oral

Primary container: 5mL bottle

Volume to be administered: depends on the patient's weight

Dose: 300 mcg/kg/day

Storage conditions on the label: room temperature

Indications for administration: preferably a single dose on an empty stomach, with water.

Serious interactions: Warfarin, erdafitinib, quinidine

Control Group: Participants assigned to **placebo**, once a day for five days.

Treatment name: placebo

Drug Name: placebo

Drug Presentation: solution

Route of administration: oral

Primary container: 5mL bottle

Volume to be administered: depends on the patient's weight

Dose: same volume that would be administered of ivermectin to maintain the blind

Storage conditions on the label: room temperature

Indications for administration: same as ivermectin.

2.2. Sample size calculation

According to the literature and previous data in this study, 75% of the subjects will have the event of interest (disappearance of symptoms) by day 21. Thus, by including 390 subjects, we will identify 290 events of interest. With this sample size we will have a power of 80% and an Alpha of 0.05 to detect a Hazard ratio of 1.4 of ivermectin vs. placebo in time to symptom resolution. Taking into account a 2% follow-up loss and 76 subjects who will be excluded from the primary analysis, we will include a total of 476 subjects in the study.

3. Study Aim

To describe the efficacy of the D11AX22 (ivermectin) molecule in adults with mild COVID-19 disease

4. Outcomes

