5.1. Populations

Intention to Treat (ITT). It is the primary population of the EPIC trial and includes all patients randomized in the study. They will be analyzed according to the group assigned at the randomization visit, regardless of whether they received the medication or not.

Per protocol (PP). All patients who were adherent to the assigned intervention at the time of randomization. In addition, it includes all patients with complete data. It will be considered as a sensitivity analysis.

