6.2. Secondary outcomes

Secondary outcomes, hospitalization requirement, ICU or oxygen supplementation and deterioration in more than two points on the scale of clinical results will be analyzed through a Kaplan Meier estimate. Hazard ratio will be estimated by Cox proportional-hazard model. In addition, a logistic regression model in which each secondary outcome will be considered as the dependent variable (1: Event, 0: No event) and the intervention groups as the independent variable (1: ivermectin, 0: Placebo) will be used.

For each outcome, the odds ratio (OR) and its respective 95% CI will be reported. An OR > 1 is indicating favorable results in favor of placebo and an OR <1 in favor of ivermectin. In case of low frequency of individual outcomes, a combined variable will be created using need for hospitalization (general floor or ICU) and need for oxygen (by nasal cannula or mechanical ventilation) and will be analyzed using a logistic regression model reporting the OR with its 95% CI.

Evaluation of the effect of the treatment in each study visit using the 8-point ordinal scale will be estimated using the proportional OR with its respective 95% CI with an ordinal logistic regression. In this step, the 8-point ordinal scale will be inverted in its score, where 0 will correspond to death and 7 to a subject without symptoms. Thus, a proportional OR > 1 will indicate an effect in favor of ivermectin. The 95% confidence interval of the median difference in duration of fever and length of hospitalization or oxygen use will be estimated by bootstrap estimators.

6.3. Sensitivity Analysis and Modification of the Effect for the Primary outcome.

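### The 76 dispensing-error patients are excluded only from the primary analysis; the set for the secondary efficacy outcomes is not fixed, and the default reading dilutes the treatment contrast

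*Supplement*

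**What the plan says.** The current protocol (4.4, and the footnote to 4.5), the latest SAP (2.2) and the Amendment 4 rationale all limit the exclusion in the same way: it concerns "76 subjects who will be excluded from the primary analysis". No other analysis is mentioned. The reason is in the protocol's summary of changes under Amendment 4. Over three weeks, 38 patients randomized to placebo were given ivermectin, so that "during this period a total of 76 subjects received ivermectin and none received a placebo". The same entry says that the 76 will complete follow-up, so their secondary outcome data will exist.

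The texts that could settle their place in the secondary analyses are these:

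- SAP 5.1 says that the intention-to-treat set "includes all patients randomized in the study. They will be analyzed according to the group assigned at the randomization visit". It makes no exception for the 76. The only other set is per protocol, which SAP 6.3 uses for the primary outcome alone.
- SAP 6.2 opens with "Secondary outcomes, hospitalization requirement, ICU or oxygen supplementation and deterioration in more than two points" and goes on to the models, but names no analysis population.
- The lead-in to SAP section 6 names the intention-to-treat population, but for describing variables.
- Protocol 4.5 calls the main analysis intention to treat, yet defines the two groups by the product received.

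**The concern.** The error window contains no treatment contrast, because everyone in it took ivermectin. That is why the sponsor removed it from the primary analysis, and the reason applies equally to every other efficacy outcome. The secondary outcomes include two-point deterioration (the former primary outcome), hospitalization, oxygen use, ICU admission, clinical state by day, and fever.

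If the 76 return for these outcomes as assigned, the placebo arm contains patients treated with ivermectin and the estimates move towards no effect. If they return by product received, all 76 sit in the ivermectin group with no concurrent placebo patients. Because the plan does not choose, the choice could be made after the data are seen. The primary and secondary results might then rest on different populations without the reader being told.

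**Working it through.** **The plan's own figures.** SAP 2.2 states: "With this sample size we will have a power of 80% and an Alpha of 0.05 to detect a Hazard ratio of 1.4". Two-sided alpha is assumed, as sidedness is not given.

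- Freedman: events = 7.849 × (2.4/0.4)² = 283. Schoenfeld: 4 × 7.849/(ln 1.4)² = 278. With 290 events, Schoenfeld power is 0.817. The stated 290 is reproduced to within 3% by Freedman.
- At the stated 75% event proportion, 390 × 0.75 = 292.5, against the plan's "by including 390 subjects, we will identify 290 events of interest".
- Allowing for 2% loss, 390/0.98 = 398, and 398 + 76 = 474. The plan has 476, which is 400 + 76.

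So the sizing rests on about 400 patients outside the window, or 200 per arm. The sample size is not in dispute.

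**Misclassified share if all 476 are analysed as assigned.** With 1:1 allocation there are 238 per arm. The 38 come from the Amendment 4 rationale. 38/238 = 0.160.

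**Effect on the estimates.** Let p₀ and p₁ be the placebo and ivermectin risks. The risk in the placebo-assigned arm becomes (200·p₀ + 38·p₁)/238. The risk difference is multiplied by 200/238 = 0.840, a shrinkage of 16.0% at any event rate. SAP 6.2, however, reports odds ratios and hazard ratios. Power below is Φ[(Δ − 1.96·SE₀)/SE₁], with SE₀ from the pooled risk and SE₁ from the separate risks. The risks are assumptions.

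| Assumed risk, placebo vs ivermectin | Placebo risk, diluted | Odds ratio, clean → diluted | Log-OR shrinkage | Power, 200 per arm, 76 out | Power, 238 per arm, 76 in as assigned |
|---|---|---|---|---|---|
| 30% vs 20% | 28.4% | 0.583 → 0.630 | 14.3% | 0.638 | 0.572 |
| 20% vs 10% | 18.4% | 0.444 → 0.493 | 12.7% | 0.802 | 0.749 |
| 10% vs 5% | 9.2% | 0.474 → 0.519 | 12.3% | 0.475 | 0.430 |
| 5% vs 2.5% | 4.6% | 0.487 → 0.532 | 12.2% | 0.259 | 0.235 |
| 3% vs 1.5% | 2.8% | 0.492 → 0.536 | 12.1% | 0.171 | 0.157 |

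For the 20% vs 10% row, the diluted risk is (200 × 0.20 + 38 × 0.10)/238 = 43.8/238 = 0.184.

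For time-to-event outcomes, a simulated Cox model with a true hazard ratio of 0.5 and 5% placebo risk by day 21 gives about 0.54, a log-hazard-ratio shrinkage of about 11%.

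**Why power falls with more patients.** On the difference scale the signal-to-noise ratio changes by about 0.840 × √(476/400) = 0.917. The 19% gain in patients does not make up for the lost contrast.

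**Grouping by product received.** This gives 238 + 38 = 276 on ivermectin and 238 − 38 = 200 on placebo. Nominal power at 20% vs 10% would be higher (0.861), but the 38 sit in a group to which they were not randomized, and the window contributes to one group only. Any drift in case mix or event rate over calendar time then enters the comparison.

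**The case against.** A reader might infer that the plan prescribes secondary analyses on all randomized patients as assigned. It does not. SAP 6.2 names no set, and protocol 4.5 would, read literally, put the 38 in the ivermectin group. Primary analysis could also mean the main analysis set for every outcome. The Amendment 4 rationale lends this some support, since it adds 76 patients to keep the planned 400. SAP 5.1 read to the letter even contradicts excluding the 76 from the primary analysis, so it cannot be decisive for the secondary outcomes alone. This objection stands as far as it goes: the diluted analysis is a default reading, not an instruction. But the remedy is still needed, because three readings are open and the text does not choose among them.

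It can also be said that analysing everyone as assigned is standard and conservative, and that excluding randomized patients needs justification. That is fair, and a reason to show the 476 as a supplement. Here, though, the exclusion follows a calendar window across both arms and not patient outcome, and the sponsor has already accepted it for the primary outcome.

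Lastly, the loss is small where events are rare. The summary of changes reports two-point deterioration in under 3% of patients, and at such rates power is very low either way. This too stands.

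**Conclusion.** The concern holds as one of an unspecified analysis set with unreconciled texts. If all 476 are analysed as assigned, 16% of the placebo arm took ivermectin. Secondary effects then shrink by 16% on the risk difference and by about 11-14% on the log odds ratio or log hazard ratio. It would be tempting to say that any effect shrinks by 16%, but that is exact only for an absolute difference, and SAP 6.2 reports ratios. Nor does the power loss apply evenly: it is about 5 points at 20% versus 10%, and about 1 point at 3% versus 1.5%.

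These sizes assume exactly 238 per arm, no loss to follow-up, a full ivermectin effect in the 38, and event rates that the documents do not supply. The sample size calculation is untouched. The matter should be settled before the secondary outcomes are analysed, since the two readings that keep all 476 are each worse than carrying the primary set through.

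**What to change.** - In SAP 5.1, define the main efficacy set as all patients randomized outside the three-week error window, analysed as assigned, and give the window's dates. This also removes the conflict between the present definition and the exclusion in SAP 2.2.
- In SAP 6.2, state that all secondary efficacy analyses use that set.
- Report the secondary outcomes in all 476 as assigned, as a supplementary analysis labelled as such.
- In protocol 4.5, replace or explain the grouping by product received so that it agrees with the above.

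The cost is a few sentences, one extra set of tables, and 76 fewer patients in the main secondary tables. In the scenarios above, power for those outcomes does not fall as a result; it rises slightly or stays about the same compared with 476 as assigned.
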